## 1.0 Schema

### Recruit 104 Women with Atypical Hyperplasia (ADH, ALH), LCIS or Increased Breast Cancer Risk

Targeted Accrual: 42 at Mayo Clinic Rochester, 42 at Northwestern University, and 20 at MD Anderson Cancer Center at Cooper

## Definitions

Generic name: Tamoxifen Brand name(s): Nolvadex, Soltamox Availability: MRI Global	Generic name: Topical 4-OHT Brand name(s): NA Availability: BHIR Pharma, LLC
------------------------------------------------------------------------------------------	------------------------------------------------------------------------------------

## 2.0 Background

We plan to prospectively study breast tissue changes after a short course of Tamoxifen (Tam). Women with atypical hyperplasia (AH) and lobular carcinoma in situ (LCIS) are at increased risk of breast cancer (BC) (~1-2 % per year). Over two decades ago, placebo-controlled randomized trials established that oral tamoxifen (20 mg/day) reduces breast cancer risk by 50% in generally defined high risk women, with ~70% reduction in women at high risk specifically due to atypical hyperplasia.[1] Years later, the side effects and toxicity of oral tamoxifen at 20 mg/day remain a significant barrier to its uptake and long-term compliance.[2, 3] To address the issue of toxicity, two main strategies have been pursued: 1) using a lower dose of oral tamoxifen, and 2) using a topical formulation of tamoxifen to avoid systemic side effects. Here we will perform a prospective study of women with AH, LCIS, or increased risk of BC based on risk model calculations concordant with current consensus guidelines (described in detail below) who will take a short course of prevention therapy; breast tissue samples will be evaluated pre- and post-therapy to identify and evaluate very early biomarkers of response. The overall goal of the study is to evaluate short- term changes in background breast tissue induced by either low-dose oral tamoxifen or topical 4-OHT gel in women with AH, LCIS, or increased risk of BC based on risk model calculations.

### **4hydroxytamoxifen (4-OHT) gel is a novel formulation of tamoxifen with local tissue absorption and less toxicity.**

Recent experience with 4-hydroxytamoxifen gel (4-OHT) gel shows promise for improved local breast tissue absorption and efficacy, with low systemic toxicity. 4-OHT is an active tamoxifen metabolite. 4-OHT and another tamoxifen metabolite, endoxifen, are known to account for the anti-cancer activity of tamoxifen.[4] 4-OHT has greater affinity for the ER $\alpha$  receptor and better suppression of normal and BC cell growth *in vitro* than tamoxifen. [5-8] Transdermal 4-OHT is locally absorbed at effective doses. Human and animal studies show that transdermal delivery of 4-OHT via gel applied to the breast skin results in local absorption and concentration in breast tissue. [9-12] Compared to oral tamoxifen (20 mg dose), transdermal 4-OHT delivery achieves equivalent tissue doses with a simultaneous 80% reduction in plasma levels. [9, 13] In clinical trials, 4-OHT gel results in Ki67 reduction with less toxicity. In neoadjuvant window trials in DCIS and invasive BC, women treated with two to ten weeks of 4-OHT gel (2 mg/breast/day) versus oral tamoxifen (20 mg/day) show similar decreases in cellular proliferation (50-60%) assessed by Ki67.[9, 13] The elevation of serum coagulation proteins seen in patients taking oral tamoxifen does not occur in patients treated for the same time period with 4-OHT gel,[9] and patients report fewer vasomotor symptoms with 4-OHT.[14]

### **Low-dose (5 mg/day) oral tamoxifen shows similar efficacy to standard historical dose (20 mg/day) for breast cancer prevention, with few side effects.**

Reducing the dose of oral tamoxifen is another alternate strategy to address toxicity and poor compliance with standard oral tamoxifen (20 mg/day), with a recently published trial by deCensi et al showing similar reductions in breast cancer risk with an approximate 5 mg/day dose (actually taken as 10 mg every other day or a split pill every day).[15] Minimum effective dose biomarker studies showed that 5 mg/day was not inferior to 20 mg/day in inhibiting breast cancer proliferation [16] and a prospective cohort study showed that 10 mg every other day reduced DCIS recurrence by 50%. [17] Based on these findings, a Phase III placebo-controlled randomized trial was undertaken to evaluate the efficacy of low-dose tamoxifen (~5 mg/day) for breast cancer prevention in women with breast intraepithelial neoplasia (AH, LCIS, or DCIS).[15] It is important to note that tamoxifen is not commercially available as a 5 mg pill, but rather only as a 20 mg or a 10

mg pill. Therefore, the women enrolled in this published study of low-dose tamoxifen vs placebo had the option to either take an entire pill every other day, or they could split their pills and take roughly a half of a pill every day.

Among the 500 enrolled women with median follow-up of 5.1 years, breast cancer events in either breast were reduced by approximately half (hazard ratio 0.48, p=0.02), with a 75% reduction of breast cancer events in the contralateral breast (i.e., “true” prevention; hazard ratio 0.25, p= 0.02). Patient reported toxicity for low-dose tamoxifen was similar to placebo in all symptom categories except for daily hot flashes, which were more slightly common in the tamoxifen group (2 per day) compared to the placebo group (1.5 per day). Thus, this trial of low- dose (~5 mg/day) oral tamoxifen showed a similar degree of breast cancer risk reduction, with lower toxicity, than seen in prior Phase III trials using the 20 mg/day dose of oral tamoxifen.[1] Based on the results of this recently published randomized trial of deCensi et al, low-dose tamoxifen is now recognized by ASCO as a valid alternate option for breast cancer risk reduction in women with atypical hyperplasia or LCIS.[18]

In this proposed trial we plan to utilize a reduced dose of tamoxifen (10 mg/day) as the comparator to the topical 4OHT gel intervention. There are several reasons for this approach. In the deCensi study, the ~5 mg/day oral tamoxifen resulted in breast cancer risk reduction similar to that seen in prior trials of 20 mg/day. Therefore, we expect that 10 mg/day oral tamoxifen would be at least as effective as the ~5 mg/day dose in terms of risk reduction, while likely also reducing side effects compared to the 20 mg/day dose. Given the very short (4 weeks) intervention timeframe, our primary goal is to evaluate biomarker changes. Additionally, other published studies have shown similar reductions in breast tissue proliferation markers whether the daily oral tamoxifen doses is 5 mg, 10 mg, or 20 mg, [19-21] including the biomarker Ki67 which is the primary endpoint of our proposed study. Based on the other studies described above, transdermal 4-OHT delivery should be able to achieve tissue concentrations at least equivalent to those resulting from 10 mg/day oral tamoxifen. Lastly, the study proposed here has a much shorter intervention (4 weeks), and thus compliance with dosing may have a greater effect on the planned primary endpoint (reduction in Ki67). Pill splitting would result in imprecise daily dosing and taking 10 mg every other day would increase the risk of missed doses due to a non-daily schedule. We have explored the cost of custom formulation of oral 5 mg pills and matching placebos but the cost is prohibitive (\$250,000). Therefore, we plan for oral tamoxifen 10 mg/day as the active oral drug and dosage in the comparator arm versus the 4OHT gel. We anticipate that using a 10 mg/day dose of tamoxifen in the current clinical trial will also enhance patient accrual due to expected lower side effects compared to 20 mg/day. This approach has been discussed extensively with the supporting grant program officer at NCI ([name]) and the investigational agent sponsor (Besins Healthcare), and this is judged to be the best approach, considering the many factors impacting this decision, including scientific justification, patient acceptance, feasibility, and cost.

### **The proliferation marker Ki67 is a promising biomarker of short-term response to tamoxifen.**

There is a strong rationale and existing data to support Ki67 as a biomarker in BC prevention studies. In women with AH, Ki67 in the atypia lesion is a time-dependent marker of long-term BC risk, with higher 10-year BC risk in women with Ki67 $\geq$ 2%.[22] We have also reported that Ki67 in background normal lobules in SA is associated with long-term BC risk,[23] similar to recent findings reported in the Nurses Health Study in BBD tissues.[24] Furthermore, Ki67 is also reduced after short courses of tamoxifen. In several prospective window-of-opportunity trials of Tam (ranging from 3-8 weeks of treatment), Ki67 levels in background normal breast lobules show relative reductions of ~50% with oral tamoxifen doses of 5, 10, or 20 mg per day.[19-21] Recently, we have developed a method to quantitate Ki67 (as % cells positive) in benign breast tissues using digital image assessment with Aperio algorithms. Within 40 samples, the digital image measure of Ki67 % cells positive in background normal lobules correlated very strongly with a manual pathologist score ( $r = 0.95$ ).

## Reduction in mammographic density after tamoxifen use is associated with decreased BC risk.

Tam has consistently been shown to reduce mammographic density.[25-28] Our group recently demonstrated reductions in volumetric density in breast cancer patients after one year of treatment with Tam or aromatase inhibitors.[29] Importantly, these reductions in mammographic density after prevention therapy have been shown to be associated with decreased risk of later breast cancer in high risk women taking Tam for prevention,[30] as well as reduced recurrence and mortality in breast cancer patients taking Tam as adjuvant therapy.[25-28] Thus, in the planned study we will assess change in area and volumetric density measures from mammograms to determine if changes are detectable after only one month of treatment. Early imaging changes are a feasible potential endpoint, since short-term Tam use can induce detectable breast changes with sound speed ultrasound tomography after 1-3 months,[31] on MRI within 90 days,[32] and on molecular breast imaging (MBI) at 4 weeks (**Fig 1**).

## Background Parenchymal Uptake (BPU) on MBI is a promising noninvasive imaging biomarker of response.

Molecular breast imaging (MBI) is a low-radiation dose nuclear medicine test that uses a high-resolution, semiconductor-based gamma camera to image the uptake of Tc-99m sestamibi in the breast.[33] As MBI is a functional imaging technique that relies on differences in preferential uptake of Tc-99m sestamibi in metabolically-active cells, it is able to reveal cancers hidden among dense fibroglandular tissue on a mammogram (published incremental cancer detection of 7.5-16.5 per1000 women screened).[34, 35] In addition to detecting BC, MBI also depicts the level of Tc-99m sestamibi uptake in non-cancerous background fibroglandular tissue, termed background parenchymal uptake (BPU). BPU is subjectively assessed according to a validated lexicon as one of four categories (photopenic, minimal to mild, moderate, and marked), with high reader agreement (inter-reader  $\kappa=0.84$ , intra-reader  $\kappa=0.87$ ) that describe the relative intensity of uptake in fibroglandular tissue.[36, 37] Importantly, BPU was recently shown to be associated with BC risk; women with moderate or marked BPU have 3.4 to 4.8-fold increased risk compared to women with photopenic or minimal-mild BPU, even when adjusted for percent mammographic density and hormonal influences. The exact mechanism of uptake of Tc-99m sestamibi in breast tissue is not entirely understood, but has been correlated with blood flow, mitochondrial activity, and mitotic activity in BCs.[38, 39] In a recent study led by [name], women with high BPU on screening MBI underwent 4 weeks of low-dose (5 mg or 10 mg) oral tamoxifen, with early decreases in BPU (**Fig 1**).[40] Therefore BPU is promising as a non-invasive measure of proliferative activity in the breast tissue.

[figure not shown]

Figure 1. Images from a patient with mammographically dense breasts undergoing supplemental screening with MBI (A,B) and MBI again after 4 weeks low-dose (5 mg) oral tamoxifen (C).

Mean treatment duration was 47 days for TAM and 44 days for 4OHT gel ( $p=0.2$ ). The median absolute decline in Ki67 (post-treatment compared to pre-treatment) was significant in the TAM (-3.7%,  $p<0.001$ ) but not in 4OHT gel arm (-1.3%,  $p=0.2$ ); between-arm  $p=0.002$ . Ki67 results following menopausal stratification also favored the TAM arm, especially in postmenopausal women: between-arm  $p=0.06$  in 37 premenopausal women and  $p=0.02$  in 35 postmenopausal women. Breast tissue 4OHT concentrations were lower (although not significantly) in the 4OHT arm in both superficial and deep tissue samples compared to the TAM arm (mean superficial tissue concentrations were 6.1 and 4.2 ng/g for TAM and 4OHT gel, respectively,  $p= 0.55$ ; and in deep tissues were 5.7 and 3.8 ng/g, respectively,  $p= 0.06$ ). Endoxifen (another active metabolite of tamoxifen) was abundant in plasma (11 ng/mL) and deep tissue (13 ng/g) of TAM arm, but present in only trace amounts in the 4OHT gel arm (undetectable in plasma and 0.31 ng/g in tissue), between-arm  $p <0.0001$ . Circulating TAM responsive markers (insulin like growth factor 1, sex hormone binding globulin, von Willebrand factor, and protein S total) and vasomotor symptoms were significantly and unfavorably modulated by TAM, but not by 4-OHT gel therapy.

**In summary, these trial results showed that the anti-proliferative effect of 4 mg/day transdermal 4OHT gel was inferior to 20 mg oral TAM in DCIS.** Tissue 4OHT concentration in gel treated subjects was lower, especially in deep tissues, although this did not quite reach significance ( $p=0.06$ ). Endoxifen exposure was markedly higher with oral TAM therapy and is a likely explanation for the inferiority of 4-OHT gel. The study authors recommended that in future studies, use of higher 4OHT gel doses may overcome this difference.

**Safety Data on 4OHT gel dose 8 mg/day.** Safety data is available for the 8 mg/day dose from a BHR Pharma sponsored study of 4OHT gel for reduction in breast density (BHR-700-301, see attached Investigator's Brochure February 10, 2022, pages 59-60). In this trial 149 subjects with dense breasts (BI-RADS C/D) received 8 mg/day 4OHT gel and 73 subjects received placebo for up to 52 weeks.

**Adverse Events for 8 mg/day dose.** The 149 subjects in the 4OHT gel group experienced a total of 358 AEs, and the 73 subjects in the placebo group experienced a total of 178 AEs. Overall, the incidence of AEs and treatment-related AEs was similar in both treatment groups. With regards to the non-serious AEs reported during the clinical trial, approximately 70% of the AEs that occurred in subjects receiving 4OHT gel and 74% of those in subjects receiving placebo were deemed unrelated to study treatment. Only 5% of AEs reported by the 4OHT gel group and 2.8% of AEs in the placebo group were thought to be 'probably related' to study treatment. A summary of AEs by Medical

Dictionary for Regulatory Activities (MedDRA) body system is presented on pages 59-60 in the Investigators Brochure (updated February 10, 2022).

**Serious Adverse Events with 8 mg/day dose.** Five subjects, all of whom were treated with BHR-700 4-OHT gel, experienced 1 SAE each: invasive ductal breast carcinoma (N = 2), intraductal proliferative breast lesion (N = 1), endometrial adenocarcinoma (N = 1), and pulmonary embolism (N = 1). None of the SAEs had a fatal outcome. Of the 5 reported SAEs, 3 were deemed possibly related to study treatment (invasive ductal breast carcinoma, endometrial adenocarcinoma, and pulmonary embolism). However, they could not be determined as related as there were other factors that could also have been possible causes of these events. Concerning the reported SAEs, 5 reported SAEs for 222 subjects over the reporting period of the trial is extremely low and shows the safety and tolerability of 4OHT gel. Complete details on safety data are reported in the Investigators Brochure (updated February 10, 2022).

### **Planned implementation of increased 4OHT gel dose into ongoing clinical trial**

As of 10/12/2022, 12 patients have already accrued to the trial and have been randomized to placebo, oral TAM, and 4OHT gel arms of the study. 10 have completed intervention and trial-related research studies, with 2 who have started and will complete the planned ongoing interventions. A temporary hold was placed on new enrollment on 10/12/22 so that all future patients enrolled may be treated with the higher 8 mg/day dose of 4OHT if randomized to that treatment arm.

### **Expansion of Eligibility Criteria April 2023**

In order to expand the pool of eligible patients for the trial we will include patients without atypical hyperplasia or LCIS but who are at increased risk for breast cancer based on risk model calculations that are concordant with current consensus guidelines. For women at increased risk based on Gail / Breast Cancer Risk Assessment Tool 5-year risk 3%, or International Breast Intervention Study 10-year risk 5%, breast cancer prevention therapy is RECOMMENDED (Visvanathan Journal of Clinical Oncology 2019;37(33):3152-65, NCCN Guidelines v1.2023), and therefore these women are appropriate for inclusion in this trial of short-term oral versus 4OHT topical tamoxifen. In addition, we will also allow short periods of prior use of risk-reducing medications with corresponding periods without use prior to study participation (see Exclusion criteria).

### **Database**

The study coordinators and stats team will use RAVE Medidata database for data entry. This secured database will only be accessed by study members. Each patient will be assigned a research ID for entry of data into this database. The research ID/participant name match will be kept in a secured file at each institution. Only the investigator, statisticians and study coordinators at the respective sites will have access to this file.

## **3.0 Goals**

- 3.1 Primary Aim.** Change in Ki67 from pre-treatment to post-treatment
- 3.2 Secondary Aims.** Changes from pre-treatment to post-treatment in:
  - Mammographic volumetric % density
  - Mammographic dense volume
  - Breast Cancer Prevention Trial Symptom Survey
  - Molecular Breast Imaging background parenchymal uptake
  - Changes in novel tissue biomarkers from our previous work; will be assessed with NanoString and immunohistochemistry
  - 4-OHT and metabolite levels in blood and tissue
  - Coagulation parameters

## **4.0 Patient Eligibility**

### **4.1 Screening Inclusion Criteria**

- 4.1.1** Willing to return to enrolling institution for follow-up.
- 4.1.2** Willing to complete required testing.
- 4.1.3** Ability to complete questionnaire.
- 4.1.4** Female (sex that was assigned at birth).
- 4.1.5** Age  $\geq$  18 years.
- 4.1.6** Ipsilateral intact breast with histology confirmation of atypical ductal or lobular hyperplasia, or LCIS, within the last 5 years, whether surgically excised or not; OR neither AH nor LCIS but increased breast cancer risk defined as either:
  - a)** Gail model (Breast Cancer Risk Assessment Tool) 5 year breast cancer risk of  $\geq$ 3%, or
  - b)** International Breast Intervention Study model 10 year breast cancer risk of  $\geq$ 5%.
- 4.1.7** ECOG performance status  $\leq$  1 (Karnofsky  $\geq$ 70%; see Appendix A).
- 4.1.8** The effects of topical 4-OHT gel on the developing human fetus at the recommended therapeutic dose are unknown. However, oral tamoxifen is Pregnancy Category D—positive evidence of human fetal risk. For this reason, and because triphenylethylene antiestrogens, including tamoxifen, are known to be teratogenic, women of childbearing potential and their male partners must agree to use at least one effective form of birth control (abstinence is not an allowed method) prior to study entry and for the duration of study participation, and for 2 months following the last dose of study medications (participant can resume oral birth control pills for effective birth control measures after post-treatment biopsy is done). Effective birth control methods during treatment are copper and Mirena IUD [intrauterine device], diaphragm/cervical cap/shield, spermicide, contraceptive sponge, condoms. Women of childbearing potential must have a negative pregnancy test within five days before starting study medications. Tubal Ligation is also an acceptable form of birth control. Should a woman become pregnant or suspect she is pregnant while participating in this study, she should inform her study physician immediately.
- 4.1.9** Willingness to avoid exposing breast skin to natural or artificial sunlight (i.e., tanning beds) for the duration of the study.
- 4.1.10** Participants must have acceptable organ and marrow function as judged by treating physician's evaluation of baseline laboratory data.

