Other post-treatment tests will be scheduled PRIOR to the breast biopsy but not more than 3 days prior to the post-treatment breast biopsy. The RN coordinator will instruct patient that they need to avoid pregnancy during this treatment and 2 months after treatment and instruct: The effects of topical 4-OHT gel on the developing human fetus at the recommended therapeutic dose are unknown. However, oral tamoxifen is Pregnancy Category D—Positive evidence of human fetal risk. For this reason, and because triphenylethylene antiestrogens, including tamoxifen, are known to be teratogenic, women of childbearing potential and their male partners must agree to use at least one effective form of birth control (abstinence is not an allowed method) prior to study entry and for the duration of study participation, and for two months following the last dose of study medications (participant can resume oral birth control pills for effective birth control measures after post-treatment biopsy is done). Effective birth control methods are copper and Mirena IUD (intrauterine device), diaphragm/cervical cap/shield, spermicide, contraceptive sponge, condoms; these may be used during and after treatment. Oral contraceptives may only be used after the 4-week treatment is complete, and the post-treatment biopsy is obtained. Women of childbearing potential must have a negative pregnancy test (either serum or urine pregnancy test) within five days before starting study medications. Tubal Ligation is also an acceptable form of birth control. Should a woman become pregnant or suspect she is pregnant while participating in this study, she should inform her study physician immediately.

If DCIS or invasive cancer is identified by the breast pathologist during the clinical read of the research biopsy H&E, then this information will be relayed to the assigned clinical care provider (surgeon if upcoming surgery or Breast Clinic physician if no surgery is planned).

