**9.9 Adverse Event Characteristics**

Adverse events will be collected starting at the On Study visit and ending 30 days after the post-treatment biopsy is completed. Each participant will be asked about AEs at every study visit and participant contact. AEs will be documented and logged in the RAVE Database.

CTCAE term (AE description) and grade: The descriptions and grading scales found in the revised NCI Common Terminology Criteria for Adverse Events (CTCAE) version 5.0 will be utilized for AE reporting. All appropriate treatment areas should have access to a copy of the CTCAE version 5.0. A copy of the CTCAE version 5.0 can be downloaded from the CTEP web site: <https://prevention.cancer.gov/clinical-trials/clinical-trials-management/cp-ctnet-instructions-forms>

- a. Identify the grade and severity of the event using the CTCAE version 5.0.
- b. Determine whether the event is expected or unexpected (see Section 6.11).
- c. Determine if the adverse event is related to the study intervention (agent, treatment, or procedure).
- d. Determine whether the event must be reported as an expedited report. If yes, determine the timeframe/mechanism (see Section 10.3)
- e. Determine if other reporting is required (see Section 10.0-10.2)
- f. Note: All AEs reported via expedited mechanisms must also be reported via the routine data reporting mechanisms defined by the protocol.

Note: A severe AE is NOT the same as a serious AE, which is defined in Section 10.2

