## SAE Reporting Summary

WHO	SAE	WHAT FORM	WHERE TO SEND
All sites	Pregnancy Reporting	https://prevention.cancer.gov/clinical-trials/clinical-trials-management/cp-ctnet-instructions-forms	[contact]
		MedWatch 3500A: http://www.fda.gov/downloads/AboutFDA/ReportsManualsForms/Forms/UCM048334.pdf	The Mayo Clinic Office of Research and Regulatory Support will assist Mayo Clinic Rochester in filing the MedWatch 3500A form to the FDA. Please refer to section 10.3 for reporting timelines. Mayo Clinic Rochester will report the SAE to the following: DCP Regulatory Contractor, CCS Associates: [contact]
All sites	FDA Reporting	MedWatch 3500A: http://www.fda.gov/downloads/AboutFDA/ReportsManualsForms/Forms/UCM048334.pdf	[contact]
All sites	SAEs	Mayo Clinic Department of Surgery Data and Safety Monitoring Board (DSMB)	Mayo Clinic Rochester will contact DSMB within 24 hours of notification of SAE

Mayo Clinic Rochester study team will contact the Mayo Clinic Department of Surgery (DOS) Data and Safety Monitoring Board (DSMB) within 24 hours of notification of SAE. The team will also report as indicated in section 10.2 SAE Reporting Summary.

Report the following SAE information when contacting the Mayo Clinic Department of Surgery (DOS) Data and Safety Monitoring Board (DSMB):

- Date and time of the SAE
- Date and time of the SAE report
- SAE description and attribution to drug
- Reporter name, email, and telephone number
- Affiliation/Institution where SAE occurred
- DCP and IRB protocol number
- Title of protocol

**10.2.1** An initial assessment of the SAE will be made by the DSMB. The study team will submit to the Institutional Review Board who will determine which SAEs require FDA submission as IND safety reports as noted in section 10.2.

**10.2.2** Follow-up of SAE

Mayo Clinic, Northwestern University and MD Anderson Cancer Center at Cooper will send requested follow-up reports to DCP as soon as possible. This information should be entered on the DCP SAE Report Form.

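### The request to report a pregnancy is tied to study participation and does not clearly reach the 2-month post-dose contraception window, so pregnancies late in that window may be missed

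*Combined protocol and SAP*

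**What the plan says.** Section 4.1.8 gives its reason for contraception as "oral tamoxifen is Pregnancy Category D—positive evidence of human fetal risk", together with the known teratogenicity of the drug class and the unknown fetal effects of the gel. It requires contraception "for the duration of study participation, and for 2 months following the last dose of study medications". Section 8.0 repeats the requirement and has the coordinator tell women that "they need to avoid pregnancy during this treatment and 2 months after treatment".

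Both sections carry the same reporting instruction: "Should a woman become pregnant or suspect she is pregnant while participating in this study, she should inform her study physician immediately".

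Section 9.9 sets the period for general event collection: "Adverse events will be collected starting at the On Study visit and ending 30 days after the post-treatment biopsy is completed". Participants are asked about events at each visit and contact. The Test Schedule in 5.0 has two columns, baseline and end of treatment, and the pregnancy test is marked at baseline only. Section 7.2 adds one contact at week 1.

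The SAE Reporting Summary in 10.2 has a row headed "Pregnancy Reporting" that applies to all sites. It gives a form and an address but no time limit. Section 10.3 lists congenital anomaly among the serious outcomes. At stated grades, it keeps serious events reportable beyond 30 days after the last dose if they are at least possibly related.

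**The concern.** The protocol treats the 2 months after the last dose as a period in which a conception could be harmed. A reader would expect the request to report a pregnancy to cover the same period. It is tied to participation instead, and no scheduled visit, call or test falls after the end of treatment. Detection in the post-dose period therefore depends on the woman volunteering the information, and that makes the wording of her instruction important.

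What is at stake is how completely exposed pregnancies are recorded in a blinded trial of agents that the protocol itself describes as teratogenic. Recognition lags conception, so even a conception in the first month after dosing may come to light after event collection has closed. Section 4.2.8 bars oral contraceptives for the month before the pretreatment biopsy, and section 8.0 allows them again only after the post-treatment biopsy. Some women may therefore be changing method just as follow-up ends.

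**Working it through.** The plan states no figure to reproduce here. The check is a day count followed by a comparison of sections.

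**Inputs**
- Post-dose contraception window: 2 months (4.1.8, 8.0). Two calendar months last 59 to 62 days.
- Interval from last dose to post-treatment biopsy: 0 to 2 days (5.0, 8.0).
- End of adverse event collection: 30 days after that biopsy (9.9).

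**Day count from the last dose**
- End of collection = 30 + (0 to 2) = day 30 to day 32.
- Days of the window after collection ends = window length − end of collection.
- Shortest: 59 − 32 = 27 days, and 27/59 = 45.8%.
- Longest: 62 − 30 = 32 days, and 32/62 = 51.6%.
- Mid case (61-day window, biopsy 1 day after the last dose): 61 − 31 = 30 days, and 30/61 = 49.2%.

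About half of the contraception window therefore lies after general event collection has ended.

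**A narrower reading of the participant's instruction.** If participation is taken to end at the biopsy, the instruction itself leaves between 59 − 2 = 57 of 59 days (96.6%) and the whole window unaddressed. The protocol does not define when participation ends, so this is a bound and not a finding.

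**The sections side by side**
- *What the woman is told:* 4.1.8 lists the duration of participation and then adds the 2 months as a further period. On that wording, participation does not plainly include the 2 months.
- *What prompts the site to ask:* 9.9 relies on visits and contacts. Sections 5.0 and 7.2 schedule none after end of treatment.
- *What the site does once it knows:* the pregnancy row in 10.2 applies without a time limit. Section 10.3 covers a related birth defect after 30 days at the listed grades, but pregnancy itself is not on its list of serious outcomes.

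The third step is open-ended. The first two do not clearly reach the later part of the window.

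**An undefined case.** Under 9.6, a woman stopped for a Grade 3 or higher event may decline post-treatment tissue sampling. Collection in 9.9 is counted from the biopsy, so for her it has no stated end.

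**The case against.** The strongest reply is that the 30-day limit in 9.9 is written for adverse events, and nothing says that it governs pregnancy. Section 9.8 defines an adverse event as an unfavourable symptom, sign or disease, and pregnancy has its own undated row in 10.2. The instruction in 4.1.8 and 8.0 does not say that women need report only during participation. A contraception requirement and an event-collection period serve different purposes, and both can be followed as written. Related serious events remain reportable after 30 days. The consent form, where participant instructions usually sit, was not in the copy reviewed and may already ask for reports over the full period.

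Most of this stands, and it limits the point. A reader might infer that pregnancies in the second month are excluded from reporting, or would not reach the safety data. The documents do not support that: no section closes the pregnancy route, and none forbids a later report.

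What the reply does not answer is how the site would learn of the pregnancy. Both routes that stay open begin only when the site knows. The visible protocol neither clearly asks the woman to report in that period nor schedules a contact at which she would be asked. A longer instruction in the consent form would settle the practical matter, but 4.1.8 and 8.0 would still need to match it.

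**Conclusion.** The point holds as a gap in ascertainment. Contraception is required for 2 months after the last dose, the reporting instruction is tied to participation, and general event collection ends 27 to 32 days (46% to 52% of the window) before the 2 months are over. Pregnancies in the later part of the window may therefore be missed.

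This rests on three assumptions: that the biopsy follows the last dose by 0 to 2 days as scheduled, that participation does not include the 2 months (plausible from 4.1.8 but not defined), and that the consent form does not already close the gap. The documents give neither the number of women of childbearing potential nor a conception rate, so the number of pregnancies that might be missed cannot be estimated from them.

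The matter is minor. No endpoint, sample size or power figure is affected. It is worth raising because the correction costs almost nothing.

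**What to change.** Reconcile 4.1.8, 8.0, 9.9 and the pregnancy row in 10.2 so that they state one period for pregnancy reporting.
- In 4.1.8 and 8.0, extend the participant's instruction to any pregnancy conceived during participation or during whatever post-dose contraception window the sponsor keeps, including one recognised after that window ends. Stopping the instruction on the last day of the window would miss late conceptions.
- In 9.9 and 10.2, state that pregnancies are collected on that same basis, and leave the 30-day limit for other adverse events as it is.
- In 9.9, also give an end of collection for women who have no post-treatment biopsy.
- Check the consent form and align it if its wording differs.

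The length of the contraception window is the sponsor's decision, and this change does not touch it. The cost is a phrase in 4.1.8 and 8.0, a line in 9.9, a clause in 10.2, and at most one extra message to women of childbearing potential.
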